### 5.1.5 Planned Trial Calendar

The following dates are approximate. The actual dates may differ as, for example, the trial will not start until all the appropriate regulatory and ethical approvals have been obtained.

Planned trial period (active phase) - FVFS a to LVLS b :	01 SEP 2017 to 27 OCT 2017
Planned inclusion period - FVFS to FVLS c :	01 SEP 2017 to 22 SEP 2017
Planned end of trial (LCLS d ):	04 APR 2018
Planned date of final clinical study report:	14 SEP 2018

### 5.1.6 Early Safety Data Review

This trial will not include an early review of safety data (i.e., no early safety review[s] of preliminary data occurring at pre-determined milestones defined in the protocol with pause in enrollment). However, it may be interrupted at any time if new data about the investigational product become available, and/or on advice of the Sponsor, the IRBs, or the governing regulatory authorities in the country where the trial is taking place.

If the trial is prematurely terminated or suspended, the Sponsor will promptly inform the Investigators, the IRBs, and the regulatory authorities of the reason for termination or suspension. If the trial is prematurely terminated for any reason, the Investigator will promptly inform the trial subjects and should assure appropriate therapy and follow-up.

## 5.2 Enrollment and Retention of Trial Population

### 5.2.1 Recruitment Procedures

Before the start of the trial, the Investigator or sub-investigator will contact an appropriate pool of potential subjects and invite them to participate in the study. The site will ensure that any advertisements used to recruit subjects (e.g., letters, pamphlets, posters) are submitted to Sanofi Pasteur prior to submission to the IEC / IRB for approval.

### 5.2.2 Informed Consent Procedures

Informed consent is the process by which a subject voluntarily confirms his or her willingness to participate in a particular trial. Informed consent must be obtained before any study procedures are performed. The process is documented by means of a written, signed, and dated ICF.

---

a FVFS: first visit, first subject

b LVLS: last visit, last subject

c FVLS: first visit, last subject

d LCLS: last contact, last subject (phone call at end of D180 follow-up period)

In accordance with GCP, prior to signing and dating the consent form, the subject must be informed by appropriate study personnel about all aspects of the trial that are relevant to making the decision to participate, and must have sufficient time and opportunity to ask any questions.

If the subject is not able to read and sign the ICF, then it must be signed and dated by an impartial witness who is independent of the Investigator. A witness who signs and dates the consent form is certifying that the information in this form and any other written information had been accurately explained to and understood by the subject or his / her representative.

The actual ICF used at each center may differ, depending on local regulations and IEC / IRB requirements. However, all versions must contain the standard information found in the sample ICF provided by the Sponsor. Any change to the content of the ICF must be approved by the Sponsor and the IEC / IRB prior to the form being used.

If new information becomes available that may be relevant to the subject's willingness to continue participation in the trial, this will be communicated to him / her in a timely manner. Such information will be provided via a revised ICF or an addendum to the original ICF.

Informed consent forms will be provided in duplicate, or a photocopy of the signed consent will be made. The original will be kept by the Investigator, and the copy will be kept by the subject.

Documentation of the consent process should be recorded in the source documents.

### 5.2.3 Screening Criteria

There are no screening criteria other than the inclusion and exclusion criteria.

### 5.2.4 Inclusion Criteria

An individual must fulfill *all* of the following criteria in order to be eligible for trial enrollment:

- 1) Aged  $\geq$  65 years on the day of inclusion
- 2) Informed consent form has been signed and dated
- 3) Able to attend all scheduled visits and to comply with all trial procedures

### 5.2.5 Exclusion Criteria

An individual fulfilling *any* of the following criteria is to be excluded from trial enrollment:

- 1) Participation at the time of trial enrollment (or in the 4 weeks preceding the trial vaccination) or planned participation during the present trial period in another clinical trial investigating a vaccine, drug, medical device, or medical procedure
- 2) Receipt of any vaccine in the 4 weeks (28 days) preceding the trial vaccination or planned receipt of any vaccine prior to V02
- 3) Previous vaccination against influenza (in the preceding 6 months) with either the trial vaccine or another vaccine
- 4) Receipt of immune globulins, blood or blood-derived products in the past 3 months

- 5) Known or suspected congenital or acquired immunodeficiency; or receipt of immunosuppressive therapy, such as anti-cancer chemotherapy or radiation therapy, within the preceding 6 months; or long-term systemic corticosteroid therapy (prednisone or equivalent for more than 2 consecutive weeks within the past 3 months)
- 6) Known systemic hypersensitivity to any of the vaccine components, or history of a life-threatening reaction to the vaccines used in the trial or to a vaccine containing any of the same substancesa
- 7) Thrombocytopenia or bleeding disorder, contraindicating IM vaccination based on investigator's judgment
- 8) Deprived of freedom by an administrative or court order, or in an emergency setting, or hospitalized involuntarily
- 9) Alcohol or substance abuse that, in the opinion of the investigator, might interfere with the trial conduct or completion
- 10) Chronic illness that, in the opinion of the investigator, is at a stage where it might interfere with trial conduct or completionb
- 11) Identified as an Investigator or employee of the Investigator or trial center with direct involvement in the proposed trial, or identified as an immediate family member (i.e., parent, spouse, natural or adopted child) of the Investigator or employee with direct involvement in the proposed trial
- 12) Personal or family history of GBS
- 13) Neoplastic disease or any hematologic malignancy (except localized skin or prostate cancer that is stable at the time of vaccination in the absence of therapy and subjects who have a history of neoplastic disease and have been disease free for  $\geq 5$  years)
- 14) Moderate or severe acute illness/infection (according to Investigator judgment) on the day of vaccination or febrile illness (temperature  $\geq 38.0^{\circ}\text{C}$  [ $\geq 100.4^{\circ}\text{F}$ ]). A prospective subject should not be included in the trial until the condition has resolved or the febrile event has subsided

### 5.2.6 Medical History

Prior to enrollment, subjects will be assessed for pre-existing conditions and illnesses, both past and ongoing. Any such conditions will be documented in the source document. Significant medical history (reported as diagnosis) including conditions for which the subject is or has been followed by a physician or conditions that could resume during the course of the study or lead to an SAE or to a repetitive outpatient care will be collected in the CRB. The significant medical history section of the CRB contains a core list of body systems and disorders that could be used to prompt comprehensive reporting, as well as space for the reporting of specific conditions and illnesses.

---

a The components of the QIV-HD and TIV-HD vaccines are listed in the Investigator's Brochure.

b Chronic illness may include, but is not limited to, cardiac disorders, renal disorders, autoimmune disorders, diabetes, psychiatric disorders or chronic infection.

The pertinent medical history for study purposes includes conditions belonging to the following categories:

- 1) Chronic co-morbid illnesses considered to increase the risk for influenza complications (including pre-specified diagnoses [e.g. respiratory, cardiac, blood, neurologic, kidney, and liver disorders] listed in the CRB and other significant chronic conditions, as judged by the investigator)
- 2) Other conditions (e.g., autoimmune disorders, tobacco use, residence at an assisted-living facility or nursing home within the last 6 months)

For each condition, the data collected will be limited to:

- Diagnosis (this is preferable to reporting signs and symptoms)
- Presence or absence of the condition at enrollment

The reporting of signs and symptoms is strongly discouraged.

Dates, medications, and body systems are not to be recorded, and the information collected will not be coded. Its purpose is to assist in the later interpretation of safety data collected during the trial.

#### **5.2.7 Contraindications for Subsequent Vaccination**

Not applicable since only one dose of vaccine will be administered in this trial.

#### **5.2.8 Conditions for Withdrawal**

Subjects will be informed that they have the right to withdraw from the trial at any time. A subject may be withdrawn from the study:

- At the request of the subject (dropout)

The reason for a withdrawal or dropout should be clearly documented in the source documents and on the CRB.

The Investigator must determine whether voluntary withdrawal is due to safety concerns (in which case, the reason for discontinuation will be noted as “Adverse Event” or for another reason.

Withdrawn subjects will not be replaced.

#### **5.2.9 Lost to Follow-up Procedures**

In the case of subjects who fail to return for a follow-up examination, documented reasonable effort (i.e., documented telephone calls and certified mail) should be undertaken to locate or recall them, or at least to determine their health status while fully respecting their rights. These efforts should be documented in the CRB and in the source documents.

#### **5.2.10 Classification of Subjects Who Discontinue the Trial**

For any subject who discontinues the trial prior to completion, the most significant reason for early termination will be checked in the CRB. Reasons are listed below from the most significant

to the least significant (refer to the CRF Completion Instructions for additional details and examples):

Adverse Event	To be used when the subject is permanently terminated from the study because of an AE (including an SAE), as defined in Section 9.2.2.1 .
Lost to Follow-up	To be used when the subject cannot be found or contacted in spite of efforts to locate him/her before the date of his/her planned last visit, as outlined in Section 5.2.9 . The certified letter was sent by the investigator and returned unsigned, and the subject did not give any other news and did not come to any following visit.
Protocol Deviation	To be used when the subject signed the certified letter sent by the investigator but did not give any other news and did not come to any following visit.
Withdrawal by Subject	To be used: 
 
• When the subject indicated unwillingness to continue in the study
 
• When the subject made the decision to discontinue participation in the study for any personal reason other than an SAE/AE (e.g., subject is relocating, inform consent withdrawal, etc.)
 

### 5.2.11 Follow-up of Discontinuations

The site should complete all scheduled safety follow-ups and contact any subject who has prematurely terminated the trial because of an AE, a protocol deviation, or loss of eligibility.

For subjects where the reason for early termination was lost to follow-up or if the subject withdrew informed consent and specified that they do not want to be contacted again and it is documented in the source document, the site will not attempt to obtain further safety information.

If the subject's status at the end of the study is “Withdrawal by Subject”, the site will attempt to contact them for the D180 safety follow-up except if they specified that they do not want to be contacted again and it is documented in the source document.

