***Visit 2 (D28 [+7] days after Visit 1): Collection of Safety Information and Blood Sample***

- 1) Collect and review the diary card since Visit 1, including any AEs, medications, or therapy that occurred since vaccination. The occurrence of any injection site reaction, systemic event/reaction, and/or any SAE should have been reported in the diary card.
- 2) Draw an approximately 10 mL blood sample for the titration of Abs. Note: If the attempt(s) to collect blood is (are) unsuccessful (3 attempts), the subject should be given the opportunity to return to the study site for another attempt within the visit window. If a blood sample cannot be obtained, the reason will be recorded in the blood sampling page of the CRB.
- 3) Provide the subject with a Memory Aid and review the directions for its use.
- 4) Remind the subject to expect a safety follow-up telephone call 180 days after Visit 1.
- 5) Remind the subject to report any SAE that may occur between Visit 2 and the 6-month follow-up call.
- 6) Complete the relevant CRFs for this visit.

***D180 Safety Follow-up Telephone Call (180 days [+14 days], approximately 6 months after vaccination): Collection of SAEs***

- 1) Inquire whether the subject has received any vaccinations since the last contact (to be taken into account for the collection of information in the “Concomitant Vaccination” Section (see [Section 6.7](#))).
- 2) Inquire about new occurrences of SAEs and perform follow-up on SAEs.
- 3) Explain that this will be the last contact with the site for this trial (except for subjects with SAEs that need further follow-up, as stated below).

If the first contact attempt to complete the last telephone call is unsuccessful, at least 2 separate additional attempts, conducted on different days, should be made to contact these subjects. All attempts must be documented in the subject’s source notes. If, after at least 3 documented attempts, contact cannot be established, the subject should be classified as Lost to Follow-Up (see [Section 5.2.9](#) for further details).

The exceptions for the final phone calls are:

- Subjects who voluntarily withdrew
- Subjects who have been previously classified as lost to follow-up

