### 12.2.2 Safety Analysis Set

The SafAS is defined as those subjects who have received study vaccinea. All subjects will have their safety analyzed according to the vaccine they actually received.

Safety data recorded for a vaccine received out of the protocol design will be excluded from the analysis (and listed separately).

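### Subjects classed lost to follow-up around V02 are never tried at D180 although they refused nothing, so about five months of active SAE and AESI ascertainment is given up for them

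*Protocol*

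**What the plan says.** Protocol 5.2.11 sorts subjects who stop early into three kinds.

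- Those who stopped for an AE, a protocol deviation or loss of eligibility receive all scheduled safety follow-up.
- Those who withdrew are called at D180 unless a refusal of contact is documented.
- For those lost to follow-up, and for those with a documented refusal, "the site will not attempt to obtain further safety information".

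The D180 call text in 5.1.4 agrees on the lost group. Its exceptions to the final call include "Subjects who have been previously classified as lost to follow-up".

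The class has conditions. Section 5.2.9 asks that "documented reasonable effort (i.e., documented telephone calls and certified mail) should be undertaken to locate or recall them", or at least that health status be established. Section 5.2.10 applies the class when the subject "cannot be found or contacted in spite of efforts to locate him/her before the date of his/her planned last visit", and adds: "The certified letter was sent by the investigator and returned unsigned, and the subject did not give any other news". A subject who signed for the letter but then stayed silent is classed as a protocol deviation instead.

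SAEs and AESIs are endpoints for the whole trial (9.2.2.2), and SAEs are collected to six months after vaccination (9.2.2.3.3). In the Table of Study Procedures, the D180 call is the only scheduled contact after V02. Section 12.2.2 states: "The SafAS is defined as those subjects who have received study vaccine". It sets no follow-up condition. Section 12.3.1 says that missing safety data are not replaced.

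**The concern.** The two sections agree with each other on lost subjects, so this is a design choice and not a contradiction. The difficulty is how it sits with the rest of the plan. Someone who could not be located at about day 28 is treated like someone who documented a refusal. Someone who signed a letter and never replied, or who withdrew without refusing contact, still gets a D180 attempt under 5.2.11. The documents give no reason for the difference.

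At stake is the completeness of the six-month SAE and AESI summaries. Lost subjects stay in the safety set without any active assessment after the class is assigned. If they also stay in the denominator of the six-month tables, their unobserved events lower the reported proportions. That direction does not require them to be sicker than the others. It follows from counting them while not observing them.

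**Working it through.** **Plan's own figures.** The documents give no lost-to-follow-up rate at V02. The nearest figures are in Protocol 12.5: 8% attrition for the per-protocol set, 2616 × 0.92 = 2406.7, which reproduces the stated 2407; and 5% attrition for the FAS, 2616 × 0.05 = 130.8 subjects. The FAS figure covers every reason for having no post-vaccination HAI result, so it serves as a planning ceiling for loss to follow-up.

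**Window forgone.** V02 is at D28 (+7) and the last call at D180 (+14).

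- Nominal: 180 − 28 = 152 days, 152/180 = 84% of planned follow-up, or 152/30.44 = 5.0 months.
- Shortest: 180 − 35 = 145 days (4.8 months).
- Longest: 194 − 28 = 166 days (5.5 months).

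**Subjects and person-time.** Assume a share L of 1% to 5% is lost around V02.

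| L | All (2616) | QIV-HD (1744) | Each TIV-HD (436) | Person-years forgone | Share of D0-D180 person-time |
|---|---|---|---|---|---|
| 1% | 26 | 17 | 4 | 11 | 0.8% |
| 5% | 131 | 87 | 22 | 54 | 4.2% |

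Person-years are 2616 × L × 152/365.25. The last column is L × 152/180.

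**Effect on the SAE proportion over D28-D180.** Let r be the risk in those reached and k·r the risk in those lost. If lost subjects stay in the denominator and contribute no events, the reported proportion is (1 − L)·r, and the true one is (1 − L)·r + L·k·r. The relative understatement is kL / (1 − L + kL), which does not depend on r.

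| L | k = 1 | k = 2 |
|---|---|---|
| 1% | 0.01/1.00 = 1.0% | 0.02/1.01 = 2.0% |
| 2% | 0.02/1.00 = 2.0% | 0.04/1.02 = 3.9% |
| 5% | 0.05/1.00 = 5.0% | 0.10/1.05 = 9.5% |

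**What late calls could recover.** The table compares the rule with complete ascertainment, which three calls will not achieve. If a fraction f of lost subjects is reached and their risk equals that of the lost subjects not reached, the understatement is multiplied by (1 − f). With an assumed f = 25%, at L = 5%, it falls from 5.0% to 3.8% (k = 1) and from 9.5% to 7.1% (k = 2).

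**Conditions for the class, side by side.** Section 5.1.4 classes a subject as lost after at least three documented failed attempts at the last call, and refers to 5.2.9. Sections 5.2.9 and 5.2.10 rest on calls plus certified mail, and 5.2.10 requires the returned, unsigned letter. One label therefore has two conditions.

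**The case against.** Several points on the other side stand. A reader might infer that simply missing V02 puts a subject beyond further contact. It does not: calls and certified mail must fail first. If those efforts show that an AE ended participation, that reason ranks above loss to follow-up in 5.2.10, and 5.2.11 then requires full follow-up. Known illness is in that way routed out of the class.

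A reader might also infer that lost subjects are those most likely to be ill or dead. In people aged 65 or older that is plausible for some, but an unsigned letter equally fits a move or an absence, and the documents give no reason or risk for this group. A signature, by contrast, shows a working address, which is some ground for continuing to call.

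Nor do the documents establish that lost subjects are scored as event-free. The SAP supplied is an ELLA addendum that refers analysis sets and safety derivations to a core SAP not available here; a different denominator cannot be excluded. The bar is on active attempts only: subjects are asked to report SAEs at any time, and every SAE reported during participation must be recorded. Safety is descriptive, and nothing shows that loss would differ between groups. Finally, 5.1.4 concerns the last call and 5.2.9 a missed visit, so the difference in conditions may be one of wording.

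These points limit the size and certainty of the effect. None supplies a reason for not trying again at D180.

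**Conclusion.** The point holds as an inexpensive improvement to ascertainment. For subjects who never refused contact, the plan gives up about five months (152 of 180 days) of active SAE and AESI follow-up, while keeping these subjects in the safety set. On an assumed 1-5% lost, that is 26-131 subjects and 0.8-4.2% of planned person-time. If the six-month tables use the whole safety set as denominator, SAE proportions after V02 are understated by about 1-5% in relative terms at equal risk and 2-9.5% at doubled risk.

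The loss rate, the risk ratio and the denominator are assumptions. A larger figure can be produced, for example 0.20/1.15 = 17% with 5% lost at fourfold risk, but nothing in the documents supports that risk. Most of the missingness comes from subjects being unreachable, and the rule adds only what a later attempt would have recovered. No hypothesis test or power figure is affected.

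**What to change.** 1. In Protocol 5.1.4, remove "Subjects who have been previously classified as lost to follow-up" from the exceptions to the D180 call.
2. In 5.2.11, confine the bar on further attempts to subjects with a documented refusal of contact.
3. At D180, apply the existing three-attempt rule to subjects lost around V02, and record vital status and SAEs if anyone is reached.
4. Report the number without D180 contact, by group, beside the six-month SAE and AESI tables, and state which denominator those tables use.
5. Reconcile the condition for lost to follow-up in 5.1.4 (three failed attempts) with 5.2.9 and 5.2.10 (certified letter). While 5.1.4 is open, also settle its exemption of all voluntary withdrawals, which does not match 5.2.11. That is a separate matter.

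The cost is protocol wording and up to three calls each for an assumed 26-131 subjects over about 36 centers, which is roughly one to four subjects per center (26/36 = 0.7; 131/36 = 3.6). The downside is a little site time, and many of the calls will still fail. Item 4 is useful even then, because it shows the reader how incomplete the six-month data are.

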## 5.3 Safety Emergency Call

If, as per the Investigator's judgment, a subject experiences a medical emergency, the Investigator may contact the Sponsor's RMO for advice on trial related medical question or problem. If the RMO is not available, then the Investigator may contact the Call Center —available 24 hours a day, 7 days a week—that will forward all safety emergency calls to the appropriate primary or back-up Sanofi Pasteur contact, as needed. The toll-free contact information for the Call Center is provided in the Operating Guidelines.

This process does not replace the need to report an SAE. The investigator is still required to follow the protocol-defined process for reporting SAEs to the GPE Department (Please refer to [Section 10](#)).

In case of emergency code-breaking, the Investigator is required to follow the code-breaking procedures described in [Section 6.4](#).

